In recent years with continued technological advancements, there has been enthusiasm about less invasive, and in some cases, non-invasive, tools to gauge volume status. Among these, bedside ultrasonography (performed by providers rather than sonographers) is a common tool used to evaluate the inferior vena cava (IVC) collapsibility index (CI) has been shown to be a reliable tool in adults [8]. Another non-invasive device uses a photoplethysmographic probe (CipherOx-CRI) placed on a digit to calculate the compensatory reserve index (CRI), a marker of proximity to hemodynamic collapse [9]. Both IVC CI and CRI have been shown in multiple adult studies to predict the need for volume expansion, but their utility in the pediatric population is unknown.

The goal of this proposed study is to employ the CardioQ-EDM probe to define fluid responders from non-responders among infants undergoing cranial vault reconstruction for craniosynostosis. After defining these two groups in this single arm prospective trial, we will compare the predictive utility of non-invasive devices such as the CipherOx-CRI and IVC CI to currently employed indices (heart rate, systolic blood pressure, urine output and pulse pressure variability) to gauge the need for additional fluid and ongoing resuscitation. If the CipherOx-CRI or IVC CI proved to be as predictive or better at predicting fluid responders, we hope to replace invasive arterial lines with non-invasive tools to guide resuscitation.

We chose this population for several reasons. First, CHCO performs approximately 50-70 of these cases a year making them a relatively accessible group. Second, these children are generally healthy

Protocol #: 18-2513

PI: [name]

Version date: 07/01/2019

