While numerous tools are available to guide resuscitation, one potential benefit of this project is to validate the use of CipherOx-CRI in this cohort. If CRI proves to be a valuable predictor of intravascular volume status and the need for volume expansion, this could negate the need for arterial line placement which is time consuming, invasive, and associated with complications such as arterial thrombosis. Furthermore, after validation in this cohort, additional studies could be performed in other groups of children at risk for hemorrhagic shock in the hopes to guide ongoing resuscitation accurately without the need for invasive devices.

3. Specific Aims and Hypotheses:

Aim I: Among infants undergoing cranial vault reconstruction for craniosynostosis, we aim to determine the proportion who respond to clinically administered fluid or blood products defined by pre- and post-fluid challenge $\Delta V_{Peak} > 10\%$.

Hypothesis Ia: We hypothesize that approximately half of the cohort will be fluid responsive defined by ΔV_{Peak} by $> 10\%$ after a 10 mL/kg fluid bolus is administered immediately following induction. Although this is a prediction, it is based on previous published reports suggesting a relatively even distribution among patients who clinicians believe need volume expansion. Additionally, because these children have a mean weight of 6.4 kg and will have been nil per os for several hours prior to surgery, they are at risk for intravascular volume depletion even prior to blood loss.

Hypothesis Ib: Because clinicians use pulse pressure variability, heart rate, systolic blood pressure, urine output, and blood loss to gauge need for ongoing resuscitation (either crystalloid, colloid, or blood), we suspect that more than half of subsequent fluid challenges will be given to infants who are fluid responsive (defined by a pre- and post-bolus ΔV_{Peak} of $> 10\%$).

Aim II: To determine the PPV, NPV, sensitivity, specificity, and optimal threshold for CRI, collapsibility index, pulse pressure variability, stroke volume variability, heart rate, systolic blood pressure, and mean arterial pressure as tools to predict fluid responsiveness using pre- and post-fluid challenge $\Delta V_{Peak} > 10\%$ to define fluid responders.

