Hypothesis II: CRI and collapsibility index will reliably predict fluid responsive patients with an approximate area under the receiver operating characteristic curve (AUROC) of 0.9 while other indices will have a lower predictive accuracy.

Aim III: Evaluate confounding variables that may influence predictive measures outlined in Aim II.

Hypothesis III: Confounding variables that may decrease the predictive accuracy of indices described in Aim II include spontaneous breathing over the ventilator, minimal blood loss, and hypothermia

4. Materials and Methods:

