4.5 Decision for volume expansion

All children receive a 10 ml/kg crystalloid bolus immediately after induction. The need/decision for a fluid bolus will be determined by the anesthesiologist based on clinical judgement. Currently, the anesthesiologist places an arterial line at the beginning of the case and using pulse pressure variability, HR, SBP, MAP, urine output, and blood loss determines whether or not a fluid or blood bolus is appropriate. Data collected from the CardioQ-EDM, CipherOx-CRI, and bedside ultrasound will not be provided to the care team.

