2. After positioning the patient for surgery, the CardioQ-EDM device will be placed through the mouth into the esophagus by the PI or Co-investigators (Drs. [name] or [name]) and the aortic Doppler waveform will be confirmed. Additionally, the CipherOx-CRI finger probe will be placed, and a baseline IVC CI will be measured and recorded.
3. Baseline values and measurements (included in **Table 3**) will be recorded. Additionally, the baseline ΔV_{Peak} and CRI will be recorded.
4. A protocolized 10 mg/kg crystalloid fluid bolus will be administered
5. Two minutes after the bolus has completed, repeat EDM and CRI values will be recordings and a repeat abdominal ultrasound to measure the IVC CI will be obtained.
6. If an additional fluid bolus or blood transfusion is administered during the remainder of the procedure, steps 3 and 5 will be repeated.

4.6.1 Demographic Data: Age, weight, height, body mass index (BMI), gender, and ethnicity will be collected from medical records.

4.6.2 Ventilator Data: pressure or volume control, tidal volume (ml/kg) and peak end-expiratory pressure (PEEP), peak inspiratory pressure (PIP), and spontaneously breathing.

4.6.3 CardioQ-EDM Data: Based on a validated internal nomogram derived from the child's age, height, and weight[27], peak velocities will be obtained from the Cardio-EDM monitor.

4.6.4 Fluid Data/Vasopressor Administration: Number, time, type, and volume of fluid/blood administered will be recorded in real time. Vasopressor agent, dose, and time administered will also be reported.

4.6.5 Waveform/Vital Data: As it is currently not possible to extract waveform data from the operating room monitors, we will record data in real time. Values listed below will be reported on an excel spreadsheet.

Parameters to measure:

All parameters will be measured x 3 with 30 seconds between each measurement and averaged

- Systolic blood pressure (measured by arterial line)
- Mean arterial pressure (calculated from arterial line)
- Heart rate
- Pulse pressure variability (measured by arterial line) = acquired from arterial line
- Stroke volume variability – acquired from arterial line
- $\Delta V_{peak} = (V_{Peakmax} - V_{Peakmin}) / [(V_{peakmean}] \times 100$
- Compensatory reserve index – algorithmically generated
- Inferior vena cava collapsibility index = Maximum diameter (expiration) – minimum diameter (inspiration)/maximum diameter (expiration) in M mode

4.7 Data Blinding:

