4.9.2 CardioQ-EDM Contraindications

- Doppler probes (DP240 and I2n) should not be placed in patients under 16 years of age. We will be using the KDP72 probe
- Do not use where nasal injuries are apparent or may have occurred.
- Do not use where nasal polyps exist.
- Do not use where there are circumstances of facial trauma.
- Do not use where there is a risk of brain injury.
- Do not use in patients undergoing intra-aortic balloon pumping.
- Do not use with carcinoma of the pharynx, larynx or esophagus.
- Do not use with aneurysms of the thoracic aorta.
- Do not use with tissue necrosis of the esophagus or nasal passage.
- Do not use in close proximity to laser surgery.
- Do not use in patients with pharyngo-oesophago-gastric pathology and/or severe bleeding diatheses.

5. Specific Aims:

Aim I: Define fluid responders based on aortic ΔV_{peak} : Among infants undergoing cranial vault reconstruction for craniosynostosis, we aim to determine the proportion who respond to clinically administered fluid or blood products defined by pre- and post-fluid challenge EDM $\Delta V_{Peak} >10\%$.

Mock-up Table 1: Demographics of Responders and Non-Responders to Initial 10 mL/kg bolus prior to surgical incision

Variable	Responders	Non-Responders	P-value
Demographics			
Age			
Weight			
Height			
BMI			
Gender			
Ethnicity			
Duration of NPO status			
Associated syndrome			

Legend: BMI, body mass index; npo, nil per os

Aim II: Calculate the PPV, NPV, sensitivity, specificity, and optimal threshold for CRI and collapsibility index as tools to prediction fluid responder

Protocol #: 18-2513

PI: [name]

[figure not shown]
Version date: 07/01/2019

		Fluid Responsive	
		Yes	No
CRI Threshold	+	True Positive	False Positive
	-	False Negative	True Negative

		Fluid Responsive	
		Yes	No
CI Threshold ($\geq 15\%$)	+	True Positive	False Positive
	-	False Negative	True Negative

Performance will also be calculated for heart rate, systolic blood pressure, mean arterial pressure, pulse pressure variability and stroke volume variability. Two separate analyses will be performed – one for the 10 ml/kg protocolized bolus provided immediately after induction and one accounting for all boluses provided.

Mock-up Figure

Mock-up Table 2 – Performance at predicting fluid responsiveness

Variable	Correlation (r)	AUC
IVC CI		
CRI		
SBP		
PPV		
SVV		
MAP		
HR		

Protocol #: 18-2513

PI: [name]

Version date: 07/01/2019

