Aim III: Evaluate confounding variables that may influence CRI or collapsibility index

Variable	Scale of Measurement	Data Point Location	Analysis Method
Outcome Variable IVC CI, CRI, PPV, SVV, HR, SBP, MAP AUROC	Interval	Pre-bolus measurements	
Confounding Variables Age Weight BMI Gender Ethnicity Associated syndrome Preoperative Hemoglobin Duration of NPO status Core temperature at time of bolus Paralysis provided (Y/N) Blood transfusion (Y/N) Total blood volume Total Crystalloid Total Colloid Vasopressor requirement Total amount of vasopressor Ventilation Tidal volume PEEP PIP Spontaneous breaths	Interval Interval Interval Dichotomous Ordinal Dichotomous Interval Interval Interval Dichotomous Dichotomous Interval Interval Interval Dichotomous Interval Interval Dichotomous	Demographics Demographics Demographics Demographics Demographics Demographics Demographics Preop results Anesthesia Rec Anesthesia Rec Ventilator Ventilator Ventilator Ventilator	Multivariable Linear Regression

Figure or Table will depend on results found. If neither of the outcome variables are affected by the confounding variables may only report this finding in the text.

Two separate analyses will be performed – one for the 10 ml/kg protocolized bolus provided immediately after induction and one accounting for all boluses provided.

Protocol #: 18-2513

PI: [name]

Version date: 07/01/2019

Reference:

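### Hypothesis III names minimal blood loss as a factor, but the available text plans no blood-loss measurement at each bolus, so this part cannot be tested per bolus and bleeding between readings goes unseen after incision

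*Combined protocol and SAP*

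**What the plan says.** Section 3, Hypothesis III, lists three factors that may reduce the accuracy of the indices; they "include spontaneous breathing over the ventilator, minimal blood loss, and hypothermia". Hypothesis Ib and section 4.5 also treat blood loss as relevant and as known in the operating room. Hypothesis Ib begins "Because clinicians use pulse pressure variability, heart rate, systolic blood pressure, urine output, and blood loss to gauge need for ongoing resuscitation", and section 4.5 says the anesthesiologist, using arterial-line values, "urine output, and blood loss determines whether or not a fluid or blood bolus is appropriate".

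The data lists do not follow through. Section 4.6.4 covers what goes in: "Number, time, type, and volume of fluid/blood administered will be recorded in real time". Section 4.6.5 lists systolic and mean arterial pressure, heart rate, pulse pressure variability, stroke volume variability, ΔVpeak, CRI and IVC CI, under the rule "All parameters will be measured x 3 with 30 seconds between each measurement and averaged". The volume items in the Aim III table of section 5 include "Total blood volume Total Crystalloid Total Colloid", directly after the transfusion yes/no item.

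Urine output is a separate, smaller mismatch. The goal paragraph of the background compares CRI and IVC CI with "currently employed indices (heart rate, systolic blood pressure, urine output and pulse pressure variability". Aim II in section 5 says instead: "Performance will also be calculated for heart rate, systolic blood pressure, mean arterial pressure, pulse pressure variability and stroke volume variability".

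**The concern.** A factor named in a hypothesis needs a variable, a source and a time of measurement. Section 4.8 chooses confounders by screening each for univariate association with the reference standard, and a variable that is not collected cannot be screened. The background justifies the study by the need to validate these tools in hypovolemic children with substantial bleeding. Without blood loss per bolus, the report could not say how much loss its accuracy estimates apply to.

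Blood loss may also act on the reference label. A responder is defined by how far ΔVPeak falls from the pre-bolus to the post-bolus reading. If the child bleeds between the two, part of the challenge is offset and the fall may be smaller. Some responders could then be labelled non-responders, and a correct positive index reading would count as a false positive.

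**Working it through.** **Step 1: cross-check of the named factors.**

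| Factor or index | Where named | Section 4.6 lists | Section 5 lists |
|---|---|---|---|
| Spontaneous breathing | Hypothesis III | Yes (4.6.2) | Yes (Aim III table) |
| Hypothermia | Hypothesis III | No | Yes (core temperature, Aim III table) |
| Minimal blood loss | Hypothesis III | No | No |
| Urine output | Goal paragraph (as comparator) | No | No (Aim II text, mock-up Table 2, Aim III table) |

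The blood-volume row stands between transfusion yes/no and total crystalloid, so it reads as product given, not blood lost.

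**Step 2: direction of the effect on the label.** The background text around Figure 2 says that more respiratory variation goes with less intravascular volume. Section 4.4 takes ΔVPeak before minus ΔVPeak after, with a threshold of 10%. Bleeding between readings raises the second term, so the difference shrinks. The direction therefore follows from the plan's own definitions.

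**Step 3: which boluses.** Section 4.7 says the first bolus precedes incision, so surgical bleeding cannot affect it. Section 5 analyses that bolus separately. The issue is confined to post-incision boluses, which enter Hypothesis Ib and the all-bolus analyses.

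**Step 4: possible size.** Inputs from the protocol:
- mean weight 6.4 kg (Hypothesis Ia);
- bolus 10 to 20 ml/kg within 10 minutes (4.4);
- post-bolus reading 5 minutes after completion (4.4), or 2 minutes (4.6, step 5, repeated for later boluses by step 6).

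The longest window is therefore 10 + 2 = 12 or 10 + 5 = 15 minutes; a faster bolus shortens it. Volumes are 6.4 × 10 = 64 ml and 6.4 × 20 = 128 ml. Bleeding rates are assumptions.

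Share offset = rate × window / bolus volume.

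| Assumed rate | Loss in 12 min | Share of 64 ml | Share of 128 ml | Loss in 15 min | Share of 64 ml | Share of 128 ml |
|---|---|---|---|---|---|---|
| 0.5 ml/min | 6 ml | 9% | 5% | 7.5 ml | 12% | 6% |
| 1 ml/min | 12 ml | 19% | 9% | 15 ml | 23% | 12% |
| 2 ml/min | 24 ml | 38% | 19% | 30 ml | 47% | 23% |
| 4 ml/min | 48 ml | 75% | 38% | 60 ml | 94% | 47% |

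The top rate is an extreme: 4 / 6.4 = 0.625 ml/kg/min. With a lower assumed range of 0.05 to 0.4 ml/kg/min, the share of a 10 ml/kg bolus runs from 0.05 × 12 / 10 = 6% to 0.4 × 15 / 10 = 60%.

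**Step 5: what mislabelling would do, as illustration only.** Let p be the true responder share and m the assumed share of responders mislabelled, independently of the index. The observed share is p(1 − m). Among labelled non-responders, w = pm / (1 − p + pm) are really responders. With a true AUROC of 0.9 (Hypothesis II), the observed AUROC = 0.9(1 − w) + 0.5w.

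- p = 0.5, m = 0.1: share 0.45; w = 0.05 / 0.55 = 0.091; AUROC 0.86.
- p = 0.5, m = 0.2: share 0.40; w = 0.10 / 0.60 = 0.167; AUROC 0.83.
- p = 0.6, m = 0.2: share 0.48; w = 0.12 / 0.52 = 0.231; AUROC 0.81.

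In the last case, a true majority of responders would be seen as a minority, against Hypothesis Ib. The documents give no value for m.

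**The case against.** The strongest reply is that absence is not proved. The Data Collection Form and Table 3 are cited but are not in the text. Section 4.6 is plainly not exhaustive: core temperature, fasting duration, preoperative hemoglobin and paralysis are in the Aim III table but not in 4.6. That table also names the anesthesia record as a source. This stands as a limit. A reader might infer that blood loss will not be recorded at all; the documents support only that the available text does not list it. The point survives because the Aim III table holds the other two Hypothesis III factors and omits this one, and because a case total would not place the loss at a given bolus.

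A reader might also infer that a planned urine-output comparison has become impossible. Urine output is a comparator only in the goal paragraph. Aim II, its analysis text and mock-up Table 2 never include it, and Hypothesis Ib names it only as a reason for giving fluid. It also fits poorly with three readings 30 seconds apart. This is a wording mismatch between goal and aim.

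Finally, the plan has a crude handle on minimal blood loss, since the pre-incision bolus is analysed separately. But comparing that bolus with later ones mixes blood loss with everything else that changes during surgery, and the second planned analysis pools all boluses.

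**Conclusion.** The point holds within limits. On the available text, the blood-loss part of Hypothesis III, one of its three named factors, cannot be tested per bolus from the planned dataset. That conclusion rests on the cross-check alone and needs no assumed figure.

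Mislabelling from bleeding is a possible bias in post-incision boluses only. Its direction follows from the plan's definitions. Its size does not: the 9% to 94% range for a 10 ml/kg bolus rests on assumed rates, the maximum bolus duration and the mean weight, and it halves at 20 ml/kg. A reader might infer that any child who bleeds during a challenge is labelled a non-responder. That happens only if the fall in ΔVPeak drops to 10% or below, and nothing in the documents says how often it would.

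**What to change.** 1. On the Data Collection Form, record the anesthesiologist's cumulative estimated blood loss (ml/kg), with the time, at each pre-bolus and post-bolus reading.
2. Add pre-bolus cumulative blood loss, with its source, as a row in the Aim III table, as the Hypothesis III factor.
3. Report an exploratory sensitivity analysis of post-incision boluses by blood loss between the two readings. It should stay exploratory, because the estimates are too imprecise for a firm exclusion cut-off.
4. Align the goal paragraph and Aim II on urine output, either by deleting it from the goal or by adding it to Aim II and mock-up Table 2.
5. Reconcile the 2-minute reading time in section 4.6, step 5, with the 5-minute time in section 4.4, since they set the length of the window.

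The cost is one timed field on a form already completed for each bolus, by an investigator who is already in the room. There are two downsides. Blood-loss estimates are imprecise in infants. The request also adds a brief exchange with the operating-room team, which section 4.7 seeks to limit; the pre-bolus request can be joined to the notice of a planned bolus that the anesthesiologist already gives under section 4.6.

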4.1 Pre-trial Training

- 1) Prior to patient enrollment, the principle investigator (PI) and two co-investigators will be trained by a certified ultrasonographer regarding how to measure the IVC CI. After participating in a one-hour skills lab, the PI and co-investigators will be evaluated for competency and reproducibility. If deemed incompetent, remediation will be required prior to the start of the trial. Additionally, we will confirm inter-observer reliability between co-investigators to assure measurement reliability.
- 2) The PI and Co-investigators (Drs. [name] or [name]) will be trained in the appropriate placement and operation of the CardioQ-EDM probe and monitor by a manufacturer representative. Given the PI's extensive experience with both nasal and oroesophageal device placement (see below), after the manufacturer representative confirms competency with appropriate probe positioning, he will be responsible for all probes placed. Prior to enrolling patients in the study, a manufacturer representative will provide a live demonstration in a child undergoing cranial vault reconstruction after informed consent.

4.2 Materials Necessary

1. Esophageal aortic Doppler (CardioQ-EDM) probe = 30 provided by Deltex Medical

Protocol #: 18-2513

PI: [name]

Version date: 07/01/2019

2. CardioQ-EDM monitor = 2 provided by Deltex Medical
3. Bedside Ultrasound = 2 machines are available in the operating room at all times
4. CipherOx CRI – Provided by Division of Pediatric Surgery

4.3 Patient recruitment

Patients will be identified by the PI based on communication with the craniosynostosis clinic team. Parents/guardians of eligible candidates will be approached by a study team member at their pre-operative appointment or on the day of surgery for voluntary participation. If recruitment is insufficient (<70%), a \$20 gift card will be used as incentive for study participation. Funding will be provided by the division of pediatric surgery if this is necessary.

4.3.1 Population: Children older than 3 months and younger than 2 years of age who undergo cranial vault reconstruction in the supine position will be included. Children with associated syndromes will be included as long as they do not have known underlying cardiac abnormalities. Consent will be translated into Spanish as well for those in whom it is indicated.

4.3.2 Exclusion Criteria: Children with known underlying cardiac anomalies or cardiac arrhythmias, infants younger 3 months of age or greater than 2 years of age. In addition, children weighing less than 3 kg will be excluded at the recommendation of the manufacturer. While vasopressor (epinephrine, norepinephrine, and/or vasopressin) support is not a contraindication, fluid boluses administered during dosage adjustments will be excluded from analysis. Patients who are placed in the prone position for surgery will also be excluded given the difficulty with obtaining a window to measure the IVC CI and possible effect on reported measurements. Additionally, if abnormal anatomy is discovered while assessing the IVC, these children will also be excluded from analysis.

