non-responders for Δ VPeak was 0.94 [18]. While the optimal Δ VPeak varied from 7-20% among studies, one of the larger series using a Δ VPeak of 10% as a threshold found the sensitivity and specificity to be 100% in distinguishing fluid responders based on aortic velocity-time integrals identified by transthoracic echocardiogram [7]. Based on these results, we plan to define fluid responders as those who have $>10\%$ Δ VPeak between pre- and post-fluid challenge.

Bedside evaluation of the IVC to calculate the CI is a commonly used tool in adults [19, 20]. It serves as a surrogate to measure preload variation induced by mechanical ventilation. The technique requires limited ultrasonographic experience often at the critical care or anesthesia fellow level. In pediatrics, the predictive utility of IVC CI has only been evaluated in small series with conflicting results [21].

The CRI is another non-invasive devise using a photoplethysmographic probe (CipherOx-CRI) placed on the index finger. Based on data gathered from the probe, a computer-generated algorithm is then used to calculate a number between zero and one, referred to the CRI (Figure 3) [22]. The CRI correlates to one's intravascular volume status and proximity to hemodynamic collapse [23].

Figure 3

Legend: CRI, compensatory reserve index. CRI=1 is normovolemia and CRI=0 is the point at which the patient is at highest risk for hemodynamic decompensation.

Confounding factors that can influence dynamic measurements must also be considered. For instance, cardiac arrhythmias, small tidal volumes, spontaneous respiration, and high positive end-expiratory pressure have been found to decrease the predictive utility of pulse pressure variability and IVC CI [24-26]. Thus, it is paramount to use and apply these measurements in the appropriate clinical setting. Presumably, the influence confounding variables have on the predictive utility of these indices in children is similar to that of adults, however, comparative analyses have not been performed. Thus, when interpreted in the appropriate clinical context, these minimally and non-invasive devices are tools available to guide a balanced fluid resuscitation; however, while small series exist in various pediatric populations, validation is necessary in order to apply these tools in hypovolemic children with significant blood loss.

Protocol #: 18-2513

PI: [name]

Version date: 07/01/2019

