4.6 Data Acquisition

If consent is obtained, a CardioQ-EDM probe will be placed on the day of surgery after induction of general anesthesia. One of the investigators will be present in the operating room for the duration of surgery to perform study procedures (PI or Co-investigators (Drs. [name] or [name]) to place all CardioQ-EDM probes) and gather study data. The anesthesiologist will inform the investigator of plans to provide a fluid or blood bolus per clinical judgement in addition to the protocolized 10 ml/kg bolus provided after induction. While the anesthesiologist is preparing to administer volume expansion, a co-investigator will collect pre-fluid bolus data. Administration of fluid will not be delayed for any reason, including performance of study measurements. Measurements will be recorded for data analysis at the completion of the trial (see below). Additionally, a CipherOx-CRI probe will be placed on the patient's index finger (again, recorded data will be interpreted post hoc) and a bedside ultrasound will be performed by either the PI or one of two co-investigators to measure the IVC CI. The IVC CI will be visualized through a sub-xiphoid window. The ultrasound

Protocol #: 18-2513

PI: [name]

Version date: 07/01/2019

indicator will be aimed at the child's left flank. Once the right atrium is identified, the ultrasound probe will be turned 90 degrees counterclockwise so the indicator is directed at the head. The best way to evaluate the IVC diameter through the respiratory cycle is to use M mode. After positioning the probe appropriately in order to visualize the IVC 2 cm inferior to the cavo-atrial junction, the M mode will be activated to measure variation in the IVC diameter with respiration. Ultrasound cine-loops will be recorded, and CI will be calculated post-hoc. Data will be recorded on the *Data Collection Form* for each fluid bolus administered. The PI and co-investigators will manage all aspects of investigational devices.

Day of Surgery Step-by-step Description:

1. While the anesthesiologist intubates and places an arterial-line, the CardioQ-EDM monitor, CipherOx-CRI device, and U/S will be set up

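### Abnormal anatomy found on the IVC scan removes the whole child from analysis, although an anomaly confined to the IVC makes only the collapsibility index unusable

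*Combined protocol and SAP*

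**What the plan says.** Section 4.3.2 lists the exclusions and ends with the rule at issue: "if abnormal anatomy is discovered while assessing the IVC, these children will also be excluded from analysis". It does not define abnormal anatomy, give a reason for the rule, or limit it to particular aims or indices.

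The same section uses a narrower unit elsewhere. For vasopressor changes, only the affected boluses go: "fluid boluses administered during dosage adjustments will be excluded from analysis". It also excludes outright "Children with known underlying cardiac anomalies or cardiac arrhythmias", while section 4.3.1 adds that "Children with associated syndromes will be included as long as they do not have known underlying cardiac abnormalities".

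The first IVC scan is on the day of surgery, after consent. In the step list of section 4.6, step 2 places the Doppler and finger probes and says that "a baseline IVC CI will be measured and recorded". The protocolized bolus is step 4 and the post-bolus measurements are step 5. The scan is repeated with any later bolus.

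Aim I is the proportion of responders. Section 5, Aim II evaluates CRI and CI and adds: "Performance will also be calculated for heart rate, systolic blood pressure, mean arterial pressure, pulse pressure variability and stroke volume variability".

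**The concern.** The rule acts after the family has consented and, on the step list, at the same step as placement of the esophageal probe. It then drops the child from everything, although most of what the study measures on that child does not come from the IVC image. Aim I loses a responder result, and the performance estimates for CRI, heart rate and the arterial-line indices each lose an observation. In the analysis of all boluses, every bolus given to that child is lost.

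Two things are at stake: some precision in a study that appears small, and the population to which the non-CI results apply. As written, whether a child counts towards the assessment of a finger probe depends on an ultrasound finding that the finger probe does not use.

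**Working it through.** **Which measurements need the IVC image**

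| Quantity | Source in the plan | Uses the IVC image? |
|---|---|---|
| Responder status (Aim I, reference for Aim II) | Esophageal Doppler peak velocity; the background says "we plan to define fluid responders as those who have" more than 10% ΔVPeak from before to after the challenge; section 4.4 gives the formula | No |
| CRI | Finger probe (background; section 4.6) | No |
| SBP, MAP, PPV, SVV | Arterial line (section 4.6.5) | No |
| HR | Vital sign (background Table 2; section 4.6.5) | No |
| CI | IVC diameter in M mode (sections 4.6 and 4.6.5) | Yes |

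Six of the seven Aim II indices, and all of Aim I, need no IVC measurement.

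**Is the exclusion really of the whole child?** The sentence names the children, and its reference to analysis is unqualified. Because the same section drops only boluses in the vasopressor case, exclusion of the child from all analyses is the natural reading. It is not spelled out aim by aim.

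**Size of the loss.** The text supplied for review gives no sample size and no frequency of abnormal anatomy, so there is no plan figure to reproduce. The inputs below are illustrative:

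- N = 30, from the number of probes in section 4.2. This is an assumption, not a stated sample size.
- Responder proportion 0.5, from Hypothesis Ia.
- AUROC 0.9, from Hypothesis II, with an even split of responders and non-responders.
- One bolus per child, as in the separate analysis of the protocolized bolus.
- 1, 2 or 3 children lost (assumed).

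*Responder proportion.* 95% half-width = 1.96 × √(0.5 × 0.5 / n). For n = 30: 1.96 × √(0.25/30) = 0.179.

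*AUROC.* Hanley-McNeil standard error = √{[A(1−A) + (m−1)(a−A²) + (m−1)(b−A²)] / m²}, with A = 0.9, m = n/2 per group, a = A/(2−A) = 0.818 and b = 2A²/(1+A) = 0.853. For m = 15 the bracket is 0.090 + 14 × 0.0082 + 14 × 0.0426 = 0.801. Then √(0.801/225) = 0.060, and 1.96 times the unrounded value is 0.117.

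| Children lost | n | Half-width, proportion | Half-width, AUROC |
|---|---|---|---|
| 0 | 30 | 0.179 | 0.117 |
| 1 | 29 | 0.182 | 0.119 |
| 2 | 28 | 0.185 | 0.121 |
| 3 | 27 | 0.189 | 0.124 |

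*How often it would matter.* The chance of at least one exclusion among 30 is 1 − (1−p)^30. The rates p below are assumed.

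| Assumed rate p | Expected exclusions | Chance of at least one |
|---|---|---|
| 0.5% | 0.15 | 14% |
| 1% | 0.3 | 26% |
| 2% | 0.6 | 45% |
| 5% | 1.5 | 79% |
| 10% | 3 | 96% |

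**The case against.** **The trigger may be wider than the IVC.** A reader might infer that abnormal anatomy affects only CI. The documents do not say so. The wording describes where the abnormality is found, not what it is, and the scan also views the heart: "Once the right atrium is identified, the ultrasound probe will be turned 90 degrees counterclockwise". Known cardiac anomalies are excluded, so the rule may partly be a backstop for an anomaly first seen in the operating room, which could affect the Doppler and arterial-line readings too. This stands. It limits the point to anomalies confined to the IVC and means that a revised rule needs a separate route for cardiac findings.

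**A common set of children is defensible.** The stated goal is to compare CRI and CI with current indices, and like-for-like comparison favors the same children throughout. Prone patients are already excluded, partly because the IVC is hard to image. This stands for head-to-head comparisons with CI, so it would be too strong to call the exclusion pointless. It does not reach Aim I or the separate performance estimates for the other six indices, which need no IVC image.

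**If the anomaly is seen at baseline, the response has not yet been measured.** On the step list this is true. But the rule removes children from analysis, not from the study. Where the plan means participation to stop, as for a malpositioned probe in section 4.9, it says so. Nothing in this rule stops the remaining measurements.

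**The effect is negligible.** At assumed rates of 0.5% or 1%, most studies of 30 would lose nobody. This is a fair argument for low priority, but not for keeping the rule.

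**Conclusion.** The point holds for anomalies confined to the IVC, and it is minor. As written, the rule discards responder status, CRI, heart rate and the arterial-line indices for a child in whom only CI is unusable. Under the assumptions above, losing 1 to 3 of 30 children widens the half-width for the responder proportion by 0.3 to 1.0 percentage points and the AUROC half-width by 0.002 to 0.007. Both the 30 and the 1 to 3 are assumptions.

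Two further readings go beyond the documents:

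- **Bias by outcome.** A reader might note that Doppler readings are visible to the study team (section 4.7), that scans are repeated after boluses, and that nobody is named to declare the anatomy abnormal. No outcome-dependent exclusion is shown, however. An anomaly seen at the baseline scan is found before the bolus response exists, and CI is calculated by a co-investigator blinded to responder status.
- **Special value of CRI in these children.** A reader might infer that CRI matters most where IVC ultrasound fails. The documents present CRI as a possible replacement for arterial lines, not as a substitute for IVC imaging.

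**What to change.** Replace the sentence in section 4.3.2 with a rule along these lines:

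*If abnormal anatomy confined to the IVC is found, IVC CI is set to missing; the child remains in Aim I and in the analyses of all other indices. A cardiac anomaly first seen on this scan is handled under the existing cardiac-anomaly exclusion. Head-to-head comparisons with CI use children with both measures, and the number affected is reported with reasons.*

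Add a short definition of abnormal anatomy so that the two routes can be told apart, and repeat the common-set rule for comparisons with CI in section 4.8.

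The cost is a few sentences, with no measurements beyond those already planned. The downside is that CI will have a different denominator from the other indices, so each result should show its own n.
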